## 9 STANDARD CARE

Patients randomized to the SC condition will be managed per standard HCV and liver disease management guidelines by the UNC hepatologists. Clinic appointments, lab tests and procedures will be conducted at the provider's discretion. Depending on severity of liver disease, patients are typically followed every 6-12 months by Hepatology. Research staff will have minimal contact with SC participants except during PRO assessment windows and two saliva sample collections. Study staff will extract clinical data from electronic medical records up to 6 months post-intervention.

## 10 VC-CBCS GROUP INTERVENTION

The CBCS is based on Cognitive Behavioral Theory (CBT) and the Informational-Motivation-Behavioral skills (IMB) theoretical framework. The intervention modules will be delivered over 14 sessions, each with a duration of 90 to 120 minutes to allow for the practice of a newly introduced skill. Each session will incorporate comprehensive information on evidence-based skills for health behavior change and stress management. The modules will also incorporate CBT skills and educational materials developed by federal agencies. Sessions will include background information and rationale, recommended behavioral skills and will utilize strategies such as peer discussion and support, goal-setting and motivational enhancement techniques to increase commitment and motivation for positive lifestyle changes.

### 10.1 Tentative Conceptual Model of the VC-CBCS

As a pilot feasibility study, we are not *testing* the intervention model depicted in [Figure 1](#) below. We are mapping out a hypothetical model to gather preparatory information to inform a subsequent efficacy trial: The model helps to identify survey items that need to be developed or used to measure intervention targets and mediators. Pilot-testing will help determine the optimal frequency of data collection of targets and mediators while balancing patient burden. Pilot-testing will help with exploration of preliminary associations (aim #4) among variables to understand their temporal relationships and strength of associations. [Figure 1](#) describes how each intervention session will attempt to target information-motivation-behavioral skills (CBT, stress management, health behaviors). Didactic information is provided to build 'buy-in'. Behavioral skills are taught and practiced during session and as homework. Sessions wrap up with round robin discussion of patients' SMART goals for the week and why a patient is motivated to work on this goal (fosters personal and social motivational enhancement, commitment, social persuasion, and healthy norms). Intervention targets may improve both psychological and physiological stress, healthy behaviors, and medication adherence, which may operate as mediators/mechanisms of change, but may also serve as intermediate outcomes in and of themselves. These mediators or intermediate outcomes may in turn, improve health outcomes, including overall health status and symptoms. It is plausible that behavioral changes and stress reduction may improve clinical disease outcomes. In this pilot study, we will attempt to collect aspartate aminotransferase (AST) and alanine aminotransferase (ALT) from patients electronic health records (EHRs) to determine the feasibility of collecting standard clinical data from the EHRs, and if

feasible, explore potential pre-post change in these two markers of liver inflammation. We will also extract additional clinical variables of interest that may be relevant to a future efficacy trial, such as hemoglobin A1C in diabetic patients (~ 20% of sample), body weight (kg) and other laboratory tests. If a future efficacy trial finds the VC-CBCS to have short-term benefits on patient outcomes, it would behoove us to investigate the potential for longer-term benefits on subjective health, liver disease, and other comorbid conditions, as has been shown in other medical populations.

**Figure 1: Conceptual Model of VC-CBCS Intervention**

## 10.2 Conducting the VC-CBCS Group Intervention

Sessions will be delivered using the UNC School of Medicine's University-approved, HIPAA-compliant WebEx® videoconferencing system. WebEx® is an application that is widely used for web and videoconferencing meetings and includes multi-point audio and video communication, screen sharing, video and audio recording, and telephone bridging. The research team will work closely with the UNC School of Medicine Information Technology Security Team on all aspects of delivering the VC-CBCS including patient instructions, iPad set up, and remote data cleaning. Each group member will join the virtual group from their home using their choice of home audio-visual technology or study-provided iPads to simultaneously observe and interact with the group facilitator and other group members ("Brady Bunch" style).

All modules follow the same three-part organization (**Table 1**):

- (1) Introduction and practice of new relaxation skill
- (2) Review of previous weeks' information, skill, and SMART goals
- (3) Information, acquisition, and practice of new skills. Didactic information is followed by practicing skills to aid in cognitive behavior change. Motivational enhancement strategies are used to increase personal and social motivation. SMART goals are used to promote achievement of weekly goals that are specific, measurable, action-oriented, realistic, and time-based.

VC-CBCS sessions will be led by a Masters-level therapist with experience in facilitating groups, protocol-based and evidence-based treatments, and adept at motivational enhancement strategies.

[figure not shown]
VC-CBCS patient materials will be stored on iPads and uploaded to a secure Google Drive shared drive containing no identifying information. Materials include the Patient Workbooks, relaxation audio-recordings, technical instructions, and link to unique REDCap application system. Hard copy *Patient Workbooks* will also be mailed to each participant prior to the first session for use during sessions.

**Table 1: Content and structure of 14 VC-CBCS group modules**

Mod	Part 1: Relaxation Training	Part 2: Review and Application of Previous Skills	Part 3: Training in New Topic and Skills
1	Progress. Muscle Relax. (PMR-6)	Introductions, Group Expectations; Confidentiality	Overview of Liver Functions, Liver Conditions, and Targets of the VC-CBCS Intervention
2	Diaphragmatic Breathing & PMR-4	Overview of Liver Functions, Liver Conditions, and Targets of the VC-CBCS Intervention	Love Your Liver: Healthy Nutrition and Hydration
3	Diaphragmatic Breathing & Mindfulness	Love Your Liver: Healthy Nutrition and Hydration	Physical Activity for the Liver
4	PMR-4 & Healing Wellness Imagery	Physical Activity for the Liver	Sleep Hygiene & Managing Sleep Problems
5	Diaphragmatic Breathing & Light Imagery	Sleep Hygiene & Managing Sleep Problems	Taking medications as prescribed & Maintaining Healthy Lifestyle
6	Deep Breathing & Immune Guided Imagery	Taking medications as prescribed & Maintaining Healthy Lifestyle	Stress Awareness & Appraisal
7	Diaphragmatic Breathing & Autogenic Training	Stress Awareness & Appraisal	Automatic Thoughts & Cognitive Distortions
8	PMR-4 & Self-Forgiveness Affirmation Script	Automatic Thoughts & Cognitive Distortions	Cognitive Restructuring
9	Counting Breaths & Passive PMR	Cognitive Restructuring	Coping with Stress & Symptoms
10	4-7-8 Breath & Mindful Movement	Coping with Stress & Symptoms	Cognitive-Behavioral Skills for Depression - Behavioral Activation & Pleasurable Events
11	Short Body Scan	Cognitive-Behavioral Skills for Depression – Behavioral Activation & Pleasurable Events	Activity-Rest Cycles
12	Mini Practices & Self-Acceptance Affirmation Script	Activity-Rest Cycles	Anger Prevention & Management
13	Mindfulness Meditation & Deep Breathing	Anger Prevention & Management	Assertive Communication; Interpersonal Effectiveness
14	Group Choice	Assertive Communication; Interpersonal Effectiveness	Maintenance of Positive Lifestyle Changes & SMART Goals; Group Program Review

**Figure 2: How does the VC-CBCS help to improve Liver Health and Wellness?**

**How might group participation improve my Liver Health and Overall Health and Well-Being**

### **10.3 Technology Training and iPads and Review of Rules of Group Engagement and Privacy**

If patients do not have appropriate audio-visual technology on home computers/laptops, they will be provided a study iPad and funding for cellular or internet data plans during the duration of the study. The UNC School of Medicine Information Technology Services (ITS; <https://its.unc.edu/>) staff and the national broadband map (<https://www.broadbandmap.gov/>) will be used to determine best data plans for each participant. The iPads will be set-up and secured by SOM ITS. Participants will receive iPad, internet, and REDCap data collection training from the research staff with ITS support prior to the initial session. A conference line will be available if VC disconnection occurs. All technical issues will be tracked as part of reporting feasibility outcomes. Our consultants will share best practices for delivering tele-mental health. An SOM ITS expert will be available during each cohort launch to troubleshoot. Although patients will be provided iPad and data plans, WebEx® is available for Android and iOS smart phones. A few patients may be allowed to participate via smartphone to examine patient satisfaction and outcomes using smartphones, which could be more scalable in future projects. They can complete their post-session surveys at the conclusion of each session or at their convenience during the assessment window (7 days).

During the WebEx® training with study staff, privacy and confidentiality issues related to engagement in home-based virtual groups with other participants will be thoroughly discussed. A copy of group rules will be reviewed. Participants will need to provide verbal assurance that they will respect the group privacy rules.

### **10.4 Iterative changes to VC-CBCS intervention**

Based on patient feedback and lessons learned, the research team will modify aspects of the VC-CBCS in-between the four waves. Changes may be made based on feasibility data, patient satisfaction ratings, and impromptu feedback, feedback from exit focus groups and overall experiences and lessons learned. Consideration for making *substantial* changes during the trial would occur if major issues were identified that seriously jeopardize recruitment, attendance, retention, or data collection efforts. Otherwise, we will carefully track issues during each wave, making minor changes to improve performance, and solicit feedback about issues during exit focus groups. If recruitment, attendance, and retention are not hugely jeopardized, the team may wait to make substantive changes until after all the feasibility, patient acceptability, and exit focus group data are analyzed.

## **11 DATA COLLECTION ASSESSMENT SCHEDULE**

The data collection assessment schedule is shown in Table 2.

### **11.1 PRO Assessments**

In both conditions, PRO survey data will be collected directly from patients during the following assessment periods:

- T1: Pre-intervention (time period: Within 30 days prior to start of 1st intervention session);
- T2: After the 5th intervention session (time period: Within 21 days after the 5th session);
- T3: After the 10th intervention session (Time period: Within 21 days after the 10th session); and
- T4: At post-intervention after the 14th session (Time period: within 14 days after the 14th session).

### **11.2 Salivary Cortisol**

Saliva samples will be collected from participants in both conditions pre-intervention and post-intervention as described below. Pre-intervention time period is within 7 days prior to 1st intervention session. Post-intervention time period is within 7 days after final 14th intervention session.

### **11.3 VC-CBCS Process Assessments**

In participants assigned to the VC-CBCS condition, they will submit self-report data directly into REDCap after each of the 14 intervention sessions to collect process data. Data collected will include Patient Satisfaction/Acceptability Ratings; S-M-A-R-T (specific, measurable, action-oriented, realistic, and time-based) goals; Ratings of Importance, Motivation and Self-Confidence related to each SMART goal.

**Table 2: Data Collection Schedule**

Table 2	0	1	2	3	4	5	6	7	8	9	10	11	12	13	14
1. Study Feasibility															
# approached to consented	X														
# consented to eligible	X														
# eligible to enrolled/randomized	X														
# enrolled/randomized to retained	X														X
Randomization	X														
Session Attendance		X	X	X	X	X	X	X	X	X	X	X	X	X	X
Data Collection	X	X	X	X	X	X	X	X	X	X	X	X	X	X	X
Technology/Logistical Problems	X	X	X	X	X	X	X	X	X	X	X	X	X	X	X
2. Patient Satisfaction															
Patient Acceptability		X	X	X	X	X	X	X	X	X	X	X	X	X	X
Reasons for drop out		X	X	X	X	X	X	X	X	X	X	X	X	X	X
Group Dynamic Survey						X									X
Exit Focus Groups															X
3. Protocol Fidelity															
Facilitator Adherence		X	X	X	X	X	X	X	X	X	X	X	X	X	X
Facilitator Competence		X	X	X	X	X	X	X	X	X	X	X	X	X	X
4. Patient Features															
NINR sociodemographic data	X														
Screening information	X														X
Clinical / lab data	X														X
5. Intervention Targets	X	X	X	X	X	X	X	X	X	X	X	X	X	X	X
6a. Intermediate Outcomes/Mediators	X					X					X				X
6b. Salivary Cortisol	X														X
7a. PROs	X					X					X				X
7b. Liver enzymes / clinical data	X														X

**12 MEASURES TO EVALUATE FOUR SPECIFIC AIMS**

**12.1 Study and Intervention Feasibility (Aims #1, #2)**

To address specific aims #1 and #2, several feasibility measures will be collected from all participants. To evaluate the feasibility of conducting a larger RCT of the VC-CBCS, we will collect data on the proportion of patients who are approached/contacted by study staff ( $N^{\text{approached}}$ ) vs. consented ( $N^{\text{consented}}$ ) vs. randomized/enrolled ( $N^{\text{R/E}}$ ) vs. retained ( $N^{\text{retained}}$ ). Feasibility of data collection, EHR extraction of clinical data, and frequency and patterns of missing data on various outcomes will be evaluated (i.e., PROs, process/intermediate outcomes, salivary samples, clinical/disease outcomes). To evaluate the feasibility of delivering the intervention via video technology, we will collect feasibility data on the proportion of sessions attended by VC-CBCS participants, have patients complete a telehealth satisfaction survey, and track the frequency and nature of technical, logistical, and participant problems.

**12.2 Patient Satisfaction (Aim #3)**

To address specific aim #3, several measures of patient satisfaction will be collected. VC-CBCS patients will complete a Patient Acceptability/Satisfaction survey after each of the 14 sessions. They will complete a survey on satisfaction with therapist and group dynamics midway through and at end of the intervention. Reasons for drop out and attrition will be evaluated in both conditions. Exit group interviews will be conducted with each VC-CBCS cohort after the intervention ends and will be audio-recorded. The audio recording will be stored on a secure network server housed by UNC. The qualitative data will be analyzed to understand likes/dislikes, pros/cons, and solicit feedback on optimizing the intervention (e.g., number and duration of sessions, modules, relaxation skills, structure, group format, data collection). For the Patient Acceptability/Satisfaction Survey, items are scored on a scale from 1= not at all to 5=extremely. Data across all patients and all sessions will be averaged into a Total Patient Satisfaction

score that could range from 1 to 5 with higher scores indicating greater satisfaction. *One secondary outcome is the overall Patient Acceptability/Satisfaction survey mean score from all patients over all 14 sessions.*

### **12.3 Patient-Reported Outcome Measures (Aim #4)**

To address specific aim #4, several PRO measures will be collected to evaluate primary, secondary and exploratory outcomes to examine the temporal associations and strength of associations among variables in the preliminary conceptual described in Figure 1. PROs will be collected from all participants at four PRO time points (T1-T4). Collection of PRO data serves several preparatory functions for the efficacy trial including making final selection of PROs, contributing to sample size calculations, and exploring preliminary relationships with other variables in the causal pathway.

## **13 PRIMARY FEASIBILITY OUTCOME MEASURES**

- 13.1** Percentage of Patients Consented Versus Approached
- 13.2** Percentage of Participants Consented Versus Randomized
- 13.3** Percentage of Standard of Care Condition Participants Retained vs Enrolled
- 13.4** Percentage of VC-CBCS Intervention Condition Participants Retained vs Enrolled
- 13.5** Percentage of Surveys Completed by Participants Who Completed the Study

## **14 PRIMARY PATIENT-REPORTED OUTCOME MEASURES**

Several of the NIH Patient-Reported Outcomes Measurement System (PROMIS®) short forms will be used to measure primary outcomes such as health status, mental health symptoms, and physical health symptoms. We have found the PROMIS® surveys to have good psychometrics in HCV patients. *The primary patient-reported outcomes will be the mean T-scores at T1 (Baseline) and T4 (end of intervention):*

- 14.1** PROMIS Global Health Status Mental Health Mean T-Score
- 14.2** PROMIS Global Health Status Physical Health Mean T-Score
- 14.3** PROMIS Depression Mean T-score
- 14.4** PROMIS Anger Mean T-score
- 14.5** PROMIS Anxiety Mean T-score
- 14.6** PROMIS Fatigue Mean T-score
- 14.7** PROMIS Sleep Disturbance Mean T-score
- 14.8** PROMIS Pain Interference Mean T-score

## **15 SECONDARY PATIENT-REPORTED OUTCOME MEASURES**

**15.1 The Perceived Stress Scale Mean Score (PSS)** measures perceived stress in all participants at four PRO time points (T1-T4) and covers 30 days prior to assessment. The PSS is a widely used survey to measure stress perception. The scale includes 10 items, rated using a 5-point scale, from 0 (never) to 4 (very often) where patients report the frequency of stress symptoms in the past month. Higher PSS scores reflect higher subjective stress.

### **15.2 Sleep Behaviors**

**15.2.1** Pittsburgh Sleep Quality Index (PSQI) measures sleep behaviors and issues. All participants complete this measure at PRO time points T1 and T4 that covers 30 days prior to assessment. "During the past month, how would you rate your sleep quality overall?" The response set ranges from a minimum of 0 (Very Good) to a maximum of 3 (Very Bad). Higher mean scores indicate worse sleep quality.

**15.2.2** Pittsburgh Sleep Quality Index (PSQI) Sleep Efficiency Composite Mean Score. Items 1, 3 and 4 from the Pittsburgh Sleep Quality Index (PSQI) were used to create a Sleep Efficiency composite score. All participants completed this measure at T1 and T4 that covered 30 days prior to assessment. The sleep efficiency score = (# hours slept/# hours in bed) X 100%. The sleep efficiency composite

score ranged from: 0 = >85% efficiency, 1 = 75-84% efficiency, 2= 65-74% efficiency, and 3= <65%. Lower scores indicate better sleep efficiency.

**15.2.3 Healthy Sleep Behaviors Mean Score.** One item "In the last month, how often did you engage in healthy sleep behaviors before bedtime?" evaluated healthy sleep behaviors. All participants completed this measure at T1 and T4. The response set ranged from 0 (not at all) to 4 (almost every night). Higher scores indicated better sleep behaviors.

**15.3 Medication Adherence Visual Analog Scales** evaluate medication adherence for up to five daily medications for multiple comorbidities in the past 7 days in participants who were prescribed medications at baseline. Participants report the average adherence over the course of 7 days for each medication on a scale from 0% to 100% adherence for each medication.

**15.4 Coping Skills Confidence Mean Score:** Items from the Measure of Current Status (MOCS)-Part A will measure patient confidence in performing multiple skills including stress awareness, relaxation, assertiveness, and coping skills. The Measure of Current Status (MOCS)-Part A will measure patient confidence in performing multiple skills including stress awareness, relaxation, assertiveness, and coping skills. The scale contains 13 items rated on a scale from 0 = I cannot do this at all to 4 = I can do this extremely well. A Total Coping Skills score is created by taking the average of the 13 items where the Total Coping Skill score can range from 0 to 4.

**15.5. Alcohol and Drug Use:** Items from the Substance Abuse and Mental Illness Symptoms Screener (SAMISS) Survey evaluate self-reported alcohol use (3 items), non-prescription street drug use(1 item), and prescription drug misuse (1 item) in all participants. Individual scores could range from 0 to 4, with higher reported mean scores indicating higher consumption.

**15.6 Behavioral Risk Factor Surveillance System (BRFSS)** items measure health behaviors such as exercise; fruit, vegetable, added sugar and sweet beverage consumption; meals prepared at home in all participants at T1 (baseline) and T4 (Week 14) and will cover 30 days prior to assessment. BRFSS items were used to measure the following secondary outcomes:

- 15.6.1** Percentage of Participants Who Improved Fruit Consumption by One or More Categories
- 15.6.2** Percentage of Participants Who Improved Vegetable Consumption by One or More Categories
- 15.6.3** Percentage of Participants Who Complete Moderate Activity for at Least 10 Minutes at a Time
- 15.6.4** Mean Number of Minutes of Moderate Activity Per Week
- 15.6.5** Percentage of Participants Who Complete Vigorous Activity for at Least 10 Minutes at a Time
- 15.6.6** Mean Number of Minutes of Vigorous Activity Per Week
- 15.6.7** Mean Time Spent Sitting on the Weekdays
- 15.6.8** Mean Time Spent Sitting on the Weekends
- 15.6.9** Percentage of Participants Who Reduced Regular Soda Intake by One or More Categories
- 15.6.10** Percentage of Participants Who Reduced Diet Soda Intake by One or More Categories
- 15.6.11** Percentage of Participants Who Reduced Meals from Fast Food Restaurants by One or More Categories
- 15.6.12** Percentage of Participants Who Increased Dinners Prepared at Home by 1 or More Days

**15.7 Participant Satisfaction With VC-CBCS Intervention Mean Score:** After each VC-CBCS intervention session, participants complete a 14-item acceptability/satisfaction survey about their impressions with the current intervention session. Items are scored on a scale from 1= not at all to 5=extremely useful. Data across all VC-CBCS participants and all intervention sessions are averaged into a Total Patient Satisfaction score that could range from a minimum of 1 to a maximum of 5 with higher scores indicating greater satisfaction.

**15.8 Weight Changes.** Change in raw weight, percent weight change, and BMI evaluated among those who had pre-intervention BMI > 24.9 (overweight and above) from T1 to T4.

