## **2 STUDY AIMS**

**Aim 1:** Evaluate the feasibility of conducting a RCT of the VC-CBCS, quantified as the proportion of patients (a) approached vs. consented vs. enrolled/randomized vs. retained, and (b) who complete data collection;

**Aim 2:** Evaluate the feasibility of intervention delivery via VC, quantified as (a) the proportion of sessions attended by participants and (b) frequency and nature of technical, logistical, or participant problems;

**Aim 3:** Evaluate patient acceptability and satisfaction;

**Aim 4:** Explore changes in patient outcomes, mediators and intervention targets, as well as temporal associations and strength of associations among variables in a preliminary conceptual model, to inform a future efficacy trial.

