## **23 DATA ANALYSIS**

### **23.1 Statistical Analysis Overview**

The analysis strategies are designed to inform the feasibility and planning of a subsequent efficacy RCT. No hypothesis tests will be conducted. Statistical estimates will be reported with 95% confidence intervals (CIs) or standard deviations. Collectively, the results of this preparatory study will allow us to formulate reasonable expectations for the subsequent RCT. A publicly available PROMIS® scoring system is available for computing PROMIS T-scores. Statistical computations will be performed in SAS software (SAS Institute, Cary, NC).

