### **23.2 Aim 1: Feasibility of conducting a RCT**

Frequencies will be tabulated for the following: patients approached/called, consented, randomized/enrolled, retained, completed surveys, and salivary cortisol samples. We will examine reasons for refusal, causes of dropout, session attendance, causes and patterns of missing data, and technical and logistical difficulties with delivering the intervention via VC. *We anticipate that >50% of approached/called patients will consent; >75% of consented patients will be randomized and enroll; >80% will be retained; and >90% of PRO and cortisol data will be collected.*

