### **23.4 Aim 3: Patient satisfaction and acceptability**

Qualitative data from each exit focus groups will be obtained to help improve the structure and content of the future VC-CBCS and study methods. The Patient Acceptability/Satisfaction survey will be analyzed as an average for the 14 sessions. Items on the group dynamics survey will be evaluated at both time points. Reasons for drop out will be evaluated in both conditions. *We anticipate that patients will find the VC-CBCS highly acceptable and useful, as measured by the Patient Acceptability survey and information provided during the exit focus groups.* If 19 of the 24 VC-CBCS participants find the intervention acceptable (overall score  $\geq 3.5$  out of 5.0), the point and interval estimate will be 79% [95% CI: 61, 100].

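### Does the unstated order of averaging in the Total Patient Satisfaction score need to be fixed because early leavers might count too little?

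*Combined protocol and SAP*

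**What the plan says.** VC-CBCS participants complete a satisfaction form after each of the 14 sessions. Each form concerns the session just held (section 15.7).

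Three places describe how the forms become a score:

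- Section 15.7: "Data across all VC-CBCS participants and all intervention sessions are averaged into a Total Patient Satisfaction score", on a scale from 1 to 5.
- Section 12.2 uses nearly the same words and names as a secondary outcome the "overall Patient Acceptability/Satisfaction survey mean score from all patients over all 14 sessions".
- Section 23.4 says the survey "will be analyzed as an average for the 14 sessions". Later in the same paragraph it gives an illustration that begins "If 19 of the 24 VC-CBCS participants find the intervention acceptable (overall score" and sets that score at 3.5 or more out of 5.0. The resulting estimate is stated as 79% with limits 61 and 100.

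Section 23.1 rules out hypothesis tests and adds: "Statistical estimates will be reported with 95% confidence intervals (CIs) or standard deviations". Section 23.2 expects that ">80% will be retained". Section 23.3 expects more than 75% of VC-CBCS participants to attend more than 75% of sessions.

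**The concern.** Aim 3 is to "Evaluate patient acceptability and satisfaction", which reads as a question about participants. The text in 12.2 and 15.7 does not say in what order the averaging is done, and its plainest reading is one mean over every form returned. A person who returns 2 forms then has one seventh of the weight of a person who returns 14. Averaging session means first helps little, because an early leaver enters only the first few of them.

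If people leave because they dislike the programme, the score would mainly describe those who stayed and would overstate acceptability. The unit for the SD or confidence interval is not named either. An interval that treated forms as independent would ignore the correlation between one person's ratings and come out too narrow. Finally, 23.4 relies on an overall score per participant that 12.2 and 15.7 do not define, and nothing says how someone with no ratings is handled.

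**Working it through.** **The plan's own figure.** 19/24 = 79.2%. The one-sided exact (Clopper-Pearson) 95% lower bound is 61.1%, which with an upper limit of 100% gives the printed 61 to 100. The two-sided exact interval would be 57.8 to 92.9. The form of the interval does not bear on the order of averaging. The denominator does: the illustration counts all 24 randomised to VC-CBCS, each with one overall score.

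**Inputs from the documents.** 24 VC-CBCS participants (3.1), 14 sessions (section 10), retention above 80% (23.2).

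**Assumptions, not in the documents.** 4 of 24 leave (20/24 = 83% retained). They rate every session up to session k. The other 20 rate all 14 sessions, giving 20 × 14 = 280 forms. Leavers rate d points below stayers.

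**Combined weight of the four leavers.**

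- Participant means first: 4/24 = 0.167, whatever k is.
- Forms pooled: 4k/(280 + 4k).
- Session means first: (k/14) × (4/24).

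| Leave after | Pooled | Session means first | Participant first |
|---|---|---|---|
| session 2 | 8/288 = 0.028 | 0.024 | 0.167 |
| session 7 | 28/308 = 0.091 | 0.083 | 0.167 |

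**Difference from the participant-first mean** = d × (4/24 − weight).

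- Pooled, per point of gap: 0.167 − 0.028 = 0.139 (after session 2); 0.167 − 0.091 = 0.076 (after session 7).
- Session means first: 0.143 and 0.083.
- Pooled, d from 0.5 to 1.5: from 0.076 × 0.5 = 0.04 to 0.139 × 1.5 = 0.21.
- d = 0: no difference. Leavers 0.5 higher: −0.07 (after session 2) and −0.04 (after session 7).

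Example with stayers at 4.3 and leavers at 3.3:

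- pooled, after session 2: (280 × 4.3 + 8 × 3.3)/288 = 4.27
- pooled, after session 7: (280 × 4.3 + 28 × 3.3)/308 = 4.21
- by participant: (20 × 4.3 + 4 × 3.3)/24 = 4.13

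**If stayers also miss sessions.** With 11 of 14 rated by each stayer (220 forms), leavers after session 7 hold 28/248 = 11.3% of forms, and the difference per point falls from 0.076 to 0.054. For leaving after session 2 it is 0.167 − 8/228 = 0.132, little changed.

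**Precision.** Take total variance 1 and within-participant correlation r. The pooled standard error allowing for correlation, divided by the one that treats forms as independent, is √{[r Σn² + (1 − r)N]/N}. For leaving after session 2, N = 288 and Σn² = 20 × 196 + 4 × 4 = 3,936. At r = 0.3 this is √[(1,180.8 + 201.6)/288] = √4.8 = 2.19. It is 1.51 at r = 0.1, 2.71 at 0.5 and 3.14 at 0.7. These factors apply only if forms are treated as independent, which the plan does not propose.

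**The case for a change.** The strongest case for a change is that this is a named secondary outcome which two analysts could compute differently, and that unequal form counts are expected even if the trial meets its own expectations for retention and attendance. Reporting dropout beside the score does not alter its weights. The per-participant score in 23.4 has to be inferred. Stating the order would take a few sentences and cost little precision: over r from 0.1 to 0.7, the equal-weight mean has a standard error 0.95 to 1.10 times that of the pooled mean. Section 23.1 also wants the results to inform expectations for the later trial, where a flattering mean would be unhelpful.

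Part of this stands. The order and the unit for the SD or interval are unwritten, and the weight of very early leavers under pooling is as small as calculated.

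It does not amount to a fault in the plan, for four reasons:

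- The definition excludes no order. Read as a whole, 23.4 moves from an average over the sessions to an overall score for each of 24 people, which most naturally means each person's own average.
- Because every form rates a single session, a mean over forms answers how the sessions were received. Equal weight per participant answers another reasonable question, but it sets a mean over two modules beside a mean over fourteen. Choosing between them is a choice of target on which statisticians may differ.
- No order recovers the views of people who return no form, or leavers' views of later modules.
- The 19-of-24 sentence illustrates precision. It is not a success criterion that a shift in the mean could trip.

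**Conclusion.** No change is called for. This is missing detail on a descriptive secondary score, together with a fair choice between two summaries. With 4 of 24 leaving and a gap of 0.5 to 1.5 points, the pooled mean would exceed the participant-first mean by 0.04 to 0.21 on a 1-to-5 scale. That rests on leavers being less satisfied, which the documents do not show; with equal ratings the order is immaterial. The effect also fades with later leaving: after session 7 the leavers' pooled weight of 9.1% is already more than half of their 16.7% share.

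The narrowing of the interval by a factor of about 2.2 to 3.1 (r from 0.3 to 0.7) would need forms to be treated as independent. An analyst would normally avoid that with repeated ratings from the same people, and 23.1 allows an SD in place of an interval.

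No hypothesis test, threshold or decision depends on the mean. Readers will also see retention by arm (13.3, 13.4), patterns of missing data (12.1, 23.2), attendance (23.3), and dropout reasons and exit interviews (12.2, 23.4), so attrition cannot hide behind the score. It is enough that the analyst picks an order and names it, with its unit, in the report.
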